Appendix 5 Excluded Medications/Therapy

Excluded medications/therapy are listed in [Section 5.2](#) and [Section 6.5](#). The use of an excluded medication/therapy is a protocol violation and must be recorded in the eCRF.

Appendix 6 Contraceptive Guidance and Collection of Pregnancy Information

Definitions:

Woman of Childbearing Potential (WOCBP)

A woman is considered fertile following menarche and until becoming postmenopausal unless permanently sterile (see below).

Women in the following categories are not considered WOCBP:

1. Premenarchal
2. Premenopausal female with 1 of the following:
 - a) Documented hysterectomy.
 - b) Documented bilateral salpingectomy.
 - c) Documented bilateral oophorectomy.

Note: Documentation can come from the study center personnel's: review of the subject's medical records, medical examination, or medical history interview.
3. Postmenopausal female:
 - a) A postmenopausal state is defined as no menses for 12 months without an alternative medical cause. A high follicle stimulating hormone (FSH) level in the postmenopausal range may be used to confirm a postmenopausal state in women not using hormonal contraception or hormonal replacement therapy (HRT). However, in the absence of 12 months of amenorrhea, a single FSH measurement is insufficient.
 - b) Females on HRT and whose menopausal status is in doubt will be required to use 1 of the non-estrogen hormonal highly effective contraception methods if they wish to continue their HRT during the study. Otherwise, they must discontinue HRT to allow confirmation of postmenopausal status before study enrollment.

Contraception Guidance

Female subjects of childbearing potential are eligible to participate if they agree to use a highly effective method of contraception consistently and correctly as described in [Table 8](#) below.

Table 8 Highly Effective Contraceptive Methods

Highly Effective Contraceptive Methods That Are User Dependent^a Failure rate of < 1% per year when used consistently and correctly.

Combined (estrogen and progestogen containing) hormonal contraception associated with inhibition of ovulation^b
 
 • Oral. • Intravaginal. • Transdermal.

Progestogen only hormonal contraception associated with inhibition of ovulation
 
 • Oral. • Injectable.

Highly Effective Methods That Are User Independent^a

Implantable progestogen only hormonal contraception associated with inhibition of ovulation^b
 
 • Intrauterine device (IUD). • Intrauterine hormone-releasing system (IUS). 
Bilateral tubal occlusion.


Vasectomized partner A vasectomized partner is a highly effective birth control method provided that the partner is the sole male sexual partner of the WOCBP and the absence of sperm has been confirmed. If not, an additional highly effective method of contraception should be used.

Sexual abstinence Sexual abstinence is considered a highly effective method only if defined as refraining from heterosexual intercourse during the entire period of risk associated with the study treatment. The reliability of sexual abstinence needs to be evaluated in relation to the duration of the study and the preferred and usual lifestyle of the subject.

NOTES:

^a Typical use failure rates may differ from those when used consistently and correctly. Use should be consistent with local regulations regarding the use of contraceptive methods for subjects participating in clinical studies.

^b Hormonal contraception may be susceptible to interaction with the study treatment, which may reduce the efficacy of the contraceptive method. In this case, 2 highly effective methods of contraception should be utilized during the treatment period and for at least 30 days after the last dose of study treatment.

Pregnancy Testing:

- WOCBP will only be included in the study after a confirmed negative urine pregnancy test at Visit 2 (Baseline). The UPT must have a minimum sensitivity of 25 mIU beta human chorionic gonadotropin.
- Additional pregnancy testing will occur at times specified in the schedule of assessments during the treatment period, at the Visit 6 (EOS), and as required locally.

Collection of Pregnancy Information

Female subjects who become pregnant

- The Investigator will collect pregnancy information on any female subject who becomes pregnant while participating in this study. Information will be recorded on the appropriate form and submitted to the Sponsor within 24 hours of learning of a subject's pregnancy. The subject will be followed to determine the outcome of the pregnancy. The Investigator will collect follow-up information on the subject and the neonate, and the information will be forwarded to the Sponsor. Generally, follow-up will not be required for longer than 6 to 8 weeks beyond the estimated delivery date. Any termination of pregnancy will be reported, regardless of fetal status (presence or absence of anomalies) or indication for the procedure.
- While pregnancy itself is not considered to be an AE or SAE, any pregnancy complication or elective termination of a pregnancy will be reported as an AE or SAE. A spontaneous abortion is always considered to be an SAE and will be reported as such.
- Any post-study pregnancy related SAE considered reasonably related to the study treatment by the Investigator will be reported to the Sponsor as described in [Section 8.4.5](#). While the Investigator is not obligated to actively seek this information in former subjects, he or she may learn of an SAE through spontaneous reporting.
- Any female subject who becomes pregnant while participating in the study will be withdrawn from the study.

Appendix 7 Genetics

Use/Analysis of Deoxyribonucleic Acid (DNA)

- Genetic variation may impact a subject's response to study treatment, susceptibility to, and severity and progression of disease. Variable response to study treatment may be due to genetic determinants that impact drug absorption, distribution, metabolism, and excretion; mechanism of action of the drug; disease etiology; and/or molecular subtype of the disease being treated. Therefore, where local regulations and IRB/IEC allow, a blood/saliva/buccal sample will be collected for DNA analysis from consenting subjects.
- DNA samples will be used for research related to topical iso tretinoin for treatment of congenital ichthyosis and related diseases. Genetic research may consist of the analysis of 1 or more candidate genes or the analysis of genetic markers throughout the genome (as appropriate).
- DNA samples will be analyzed to detect transglutaminase mutations in the TGM1 gene, X-linked recessive steroid sulfatase mutations in the STS gene. Additionally, analysis may be performed to look at other genes linked to CI. Further analyses may be conducted if it is hypothesized that this may help further understand the clinical data.
- DNA samples will be analyzed using Congenital Ichthyosis XomeDxSlice to diagnose both RXLI and ARCI-LI. Additional analyses may be conducted if it is hypothesized that this may help resolve issues with the clinical data.
- The samples may be analyzed as part of a multi-study assessment of genetic factors involved in the response to study treatment or study treatments of this class to understand study disease or related conditions.
- The results of genetic analyses may be reported in the Clinical Study Report or in a separate study summary.
- The DNA samples will be handled by an independent laboratory and will be destroyed upon the completion of study. They will be in a secure storage space with adequate measures to protect confidentiality. The tests are considered Laboratory Developed Tests (LDTs) and are thus regulated per US regulations 42 CFR 493 and the laboratory is accredited by the College of American Pathologists.

Appendix 9 Dermatology Life Quality Index

DERMATOLOGY LIFE QUALITY INDEX (DLQI)

Hospital No: Date:
 Name: Score:
 Address: Diagnosis:

The aim of this questionnaire is to measure how much your skin problem has affected your life OVER THE LAST WEEK. Please tick (✓) one box for each question.

- | | | |
|--|-------------------------------------|---------------------------------------|
| 1. Over the last week, how itchy, sore, painful or stinging has your skin been? | Very much  | |
| | A lot  | |
| | A little  | |
| | Not at all  | |
| 2. Over the last week, how embarrassed or self conscious have you been because of your skin? | Very much  | |
| | A lot  | |
| | A little  | |
| | Not at all  | |
| 3. Over the last week, how much has your skin interfered with you going shopping or looking after your home or garden? | Very much  | |
| | A lot  | |
| | A little  | |
| | Not at all  | Not relevant  |
| 4. Over the last week, how much has your skin influenced the clothes you wear? | Very much  | |
| | A lot  | |
| | A little  | |
| | Not at all  | Not relevant  |
| 5. Over the last week, how much has your skin affected any social or leisure activities? | Very much  | |
| | A lot  | |
| | A little  | |
| | Not at all  | Not relevant  |
| 6. Over the last week, how much has your skin made it difficult for you to do any sport? | Very much  | |
| | A lot  | |
| | A little  | |
| | Not at all  | Not relevant  |
| 7. Over the last week, has your skin prevented you from working or studying? | Yes  | |
| | No  | Not relevant  |
| If "No", over the last week how much has your skin been a problem at work or studying? | A lot  | |
| | A little  | |
| | Not at all  | |
| 8. Over the last week, how much has your skin created problems with your partner or any of your close friends or relatives? | Very much  | |
| | A lot  | |
| | A little  | |
| | Not at all  | Not relevant  |
| 9. Over the last week, how much has your skin caused any sexual difficulties? | Very much  | |
| | A lot  | |
| | A little  | |
| | Not at all  | Not relevant  |
| 10. Over the last week, how much of a problem has the treatment for your skin been, for example by making your home messy, or by taking up time? | Very much  | |
| | A lot  | |
| | A little  | |
| | Not at all  | Not relevant  |

Please check you have answered EVERY question. Thank you.

©AY Finlay, GK Khan, April 1992 www.dermatology.org.uk, this must not be copied without the permission of the authors.

DERMATOLOGY LIFE QUALITY INDEX (DLQI) - INSTRUCTIONS FOR USE

The Dermatology Life Quality Index questionnaire is designed for use in adults, i.e. patients over the age of 16. It is self explanatory and can be simply handed to the patient who is asked to fill it in without the need for detailed explanation. It is usually completed in one or two minutes.

SCORING

The scoring of each question is as follows:

Very much	scored 3
A lot	scored 2
A little	scored 1
Not at all	scored 0
Not relevant	scored 0
Question 7, 'prevented work or studying'	scored 3

The DLQI is calculated by summing the score of each question resulting in a maximum of 30 and a minimum of 0. The higher the score, the more quality of life is impaired.

HOW TO INTERPRET MEANING OF DLQI SCORES

0 – 1	no effect at all on patient's life
2 – 5	small effect on patient's life
6 – 10	moderate effect on patient's life
11 – 20	very large effect on patient's life
21 – 30	extremely large effect on patient's life

REFERENCES

Finlay AY and Khan GK. Dermatology Life Quality Index (DLQI): a simple practical measure for routine clinical use. *Clin Exp Dermatol* 1994; 19:210-216.

Appendix 11 Itch-Numeric Rating Scale

Validated scales according to IFSI SIG / EADV Task Force Pruritus.

Contact: Center for Chronic Pruritus, University Hospital Münster.
 Email: [contact]

No license. Please reference as:
 Phan NQ et al. Acta Derm Venereol. 2012;92:502-7
 Verweyen E et al. Acta Derm Venereol. 2019;99:657-66

I. Numerical Rating Scale. On a scale from 0 (no itch) to 10 (worst imaginable itch)...

...how was your itch, on average, within the past 24 hours? Please select one number.

0	1	2	3	4	5	6	7	8	9	10
---	---	---	---	---	---	---	---	---	---	----

...how was your worst itch in the past 24 hours? Please select one number.

0	1	2	3	4	5	6	7	8	9	10
---	---	---	---	---	---	---	---	---	---	----

## 1. SCOPE OF THE STATISTICAL ANALYSIS PLAN

This Statistical Analysis Plan is an adjunct to Timber Pharmaceuticals Protocol No. 235-9051-202 Amendment 1 dated 05 August 2020. The Statistical Analysis Plan details the procedures for the statistical methods used in the presentation and analysis of the clinical study data.

## 2. ABBREVIATIONS

ADaM	Analysis Data Model
AE	Adverse event
ARCI-LI	Autosomal recessive congenital ichthyosis-lamellar ichthyosis
BSA	Body Surface Area
BMI	Body mass index
CDISC	Clinical Data Interchange Standards Consortium
CI	Congenital ichthyosis
CMH	Cochran-Mantel-Haenszel
CRF	Case report form
DEC	Dose escalation committee
DLQI	Dermatology Life Quality Index
EOS	End of Study
ICH	International Council for Harmonisation of Technical Requirements for Pharmaceuticals for Human Use
IGA	Investigator's Global Assessment
I-NRS	Itch-Numeric Rating Scale
IWRS	Interactive Web Response System
IP	Investigational Product
ITT	Intent-to-treat
LSR	Local skin reaction
MedDRA	Medical Dictionary for Regulatory Activities
MMRM	Mixed Model Repeated Measures
PP	Per-Protocol
QC	Quality control
RXLI	Recessive X-Linked ichthyosis
SAE	Serious adverse event
SAP	Statistical analysis plan
SDTM	Standard Data Tabulation Model

---

SOP	Standard operating procedure
VIIS	Visual Index for Ichthyosis Severity

### 3. RELEVANT AVANCE STANDARD OPERATING PROCEDURES AND GUIDANCES

The following Avance SOPs and regulatory guidances are relevant to this Statistical Analysis Plan:

- SOP-BIOM-0002 Clinical Data Analysis and Presentation
- SOP BIOM-0003 Blinding: Codes and Code Breaking
- SOP-BIOM-0004 Randomisation Generation
- SOP-BIOM-0009 Statistical Analysis Plans
- ICH: Statistical Principles for Clinical Trials (ICH E9, Current Step 4 version dated 5 February 1998)

### 4. INTRODUCTION

#### 4.1. Study Overview

Timber Pharmaceuticals, LLC, is developing a topical ointment (0.05% and 0.1%) formulation of isotretinoin called TMB-001 (previously PAT-001) (isotretinoin) ointment for the treatment of congenital ichthyosis (CI), including recessive X-linked ichthyosis (RXLI) and autosomal recessive congenital ichthyosis-lamellar ichthyosis (ARCI-LI) subtypes. The purpose of this study is to investigate the efficacy and safety of these two concentrations of topically applied TMB-001 in subjects 9 years of age and older.

#### 4.2. Study Objectives

- To investigate the efficacy of two concentrations of topically applied TMB-001 as a treatment for congenital ichthyosis (CI) of either the autosomal recessive congenital ichthyosis-lamellar ichthyosis (ARCI-LI) or RXLI subtypes.
- To investigate the safety of topically applied TMB-001.

#### 4.3. Study Design

This is a randomized, parallel, double-blind, vehicle-controlled study to evaluate the safety and efficacy of two concentrations of topical TMB-001 for the treatment of CI in subjects with either the ARCI-LI or RXLI subtypes.

11 study centers from United States of America and Australia are expected to participate in this global study.

The duration of treatment will be 12 weeks.

Each subject will participate in the study for up to 24 weeks (including up to a 90-day Screening period).

#### 4.4. Study Treatment

Investigational Product Name	Dosage of study medication?	Dose Frequency	Route of Administration
TMB-001	0.05%	BID	Topical
TMB-001	0.1%	BID	Topical
Vehicle Ointment (Control)	0%	BID	Topical

#### 4.5. Sample Size

This is the first study of TMB-001 using the VIIS index. No formal power calculations were performed to establish sample size since there were no VIIS response data available. A sample size of 45 subjects (15 per treatment group) has been selected to provide initial data on VIIS response and to enable formal sample size calculations for future studies, as well as to assist in dose selection for Phase 3 study.

#### 4.6. Study Endpoints

##### 4.6.1 Efficacy Endpoints

###### 4.6.1.1 Primary Efficacy:

- Proportion of subjects with VIIS "treatment success" (VIIS-50), which is defined as a 50% or greater decrease at Visit 6 (EOS) relative to Baseline in the sum of the scores for VIIS target sites that have a Baseline score of  $\geq 3$ .

###### 4.6.1.2 Key Secondary Efficacy:

- Proportion of subjects achieving IGA treatment success, where "treatment success" is defined as at least a 2-grade decrease in IGA severity score relative to Baseline at Visit 6 (EOS).

###### 4.6.1.3 Other Secondary Efficacy:

- Time to achieve VIIS-50 ( $\geq 50\%$  reduction in VIIS scaling score for body sites that had a Baseline score  $\geq 3$ ) that is maintained at the next observation.
- Changes in VIIS scaling score relative to Baseline at Visit 4 and Visit 5.
- Changes in percent BSA with CI relative to Baseline in the Treatment and Assessment Areas at Visit 3, Visit 4, Visit 5, and Visit 6 (EOS).
- Proportion of subjects with IGA "treatment success" at Visit 4, Visit 5, and Visit 6 (EOS).
- Proportion of subjects with an IGA score of 0 or 1 representing "cleared" or "almost cleared" at Visit 6 (EOS).

- Proportion of subjects with I-NRS “treatment success” where “success” is defined as at least a 4-point reduction in I-NRS relative to Baseline at Visit 6 (EOS).
- Change from Baseline in I-NRS score at Visit 6 (EOS).
- Change in DLQI from Baseline to Visit 6 (EOS).

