8.2.3 Itch-Numeric Rating Scale

Pruritus will be assessed with a self-administered Patient Reported Outcome questionnaire using the I-NRS at Visit 2 (Baseline), Visit 5, and at Visit 6 (EOS). Subjects will indicate itch severity by circling the integer that best describes the worst level of itching due to CI in the past 24 hours on an 11-point scale anchored at 0 representing “no itching” and 10 representing “worst itch imaginable.” (see [Appendix 11](#)). The study staff should review the I-NRS with each subject and

ask him/her to indicate the response that best describes his/her experience. Pruritus assessed by this evaluation should be reported as an AE only if therapy is required.

8.2.4 Percent Body Surface Area with Active Congenital Ichthyosis in the Treatment/Assessment Areas

The percent BSA with active CI within the Treatment Area will be calculated at Visit 1 (Screening). The Treatment Area includes all affected skin **excluding** the hands, face, neck, scalp and genitalia. This calculation is confirmed at Visit 2 (Baseline) and assessed at all follow-up visits. The minimum affected area to be treated will be no less than 10% and no more than 90% of the whole BSA at Visit 1 (Screening). In addition, the percent BSA with active CI within the designated VIIS /Assessment Areas will be calculated at Visit 1 (Screening) and at all follow-up visits. Note that the Treatment Area is at least equal to or larger than the VIIS Assessment Area. Based on the Treatment and VIIS Assessment Areas selected in a given subject and the extent of his/her disease, these two areas may or may not be the same. Two examples are provided below for clarity:

	Treatment Area % BSA	VIIS Assessment area % BSA
Subject 1	90% (entire body minus hands, face, neck, scalp, genitalia)	24% (upper back, upper arms, lower legs and dorsal feet)
Subject 2	70%	13% (upper back and upper arms)

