9.4.1.2 Secondary Efficacy Endpoints

The proportion of subjects achieving IGA treatment success will be the key secondary endpoint. For this endpoint, the IGA score will be dichotomized to “treatment success” or “treatment failure” where “treatment success” is defined as at least a 2-grade decrease in severity score relative to Baseline. Active treatment will be compared with vehicle at Visit 6 (EOS) using the CMH test stratified by CI subtype and 95% confidence intervals will be calculated for the difference in proportions for the treatment groups.

Additionally, one secondary endpoint is the time to achieve VIIS-50 that is maintained at the next observation. If VIIS-50 is first achieved at Visit 6 (EOS), then the endpoint is considered to have been met. A time to event analysis will be completed using the Kaplan-Meier method and log rank test to compare active treatment with vehicle.

For each of the other secondary efficacy endpoints (VIIS scaling, IGA, and I-NRS), the following summaries will be prepared at Visits 3, 4, 5, and 6 (EOS) (as applicable) by treatment group for each CI subtype and overall:

- Frequency distribution of observed scores;
- Frequency distribution of change from Baseline;
- Shift tables for changes from Baseline to Visits 3, 4, 5, and 6; and,
- Frequency distribution of treatment success rates.

Success rates between treatment groups will be compared at Visit 6 (EOS) using the CMH Test stratified by CI subtype, and 95% confidence intervals will be calculated for the difference in proportions for the treatment groups. The VIIS scaling success is defined as a $\geq 50\%$ reduction from Baseline for body sites that had a Baseline score ≥ 3 . For IGA, success is defined as a ≥ 2 -point reduction from Baseline. For I-NRS, success is defined as ≥ 4 -point reduction from Baseline.

Descriptive statistics (including mean, median, SD, min, and max) for observed and change from Baseline values in the DLQI and percent BSA affected in the Treatment/Assessment Areas at each visit will be presented by treatment group for each CI subtype and overall.

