## 6. ANALYSIS POPULATIONS

### 6.1. Intent-to-Treat (ITT) Population

All randomized subjects who received at least one dose of study medication will be included in the ITT population. Subjects will be analysed according to the treatment they are planned to receive according to the randomization schedule. The ITT population will be used for the analysis and presentation of all efficacy data.

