### 9.1.3. I-NRS

I-NRS scores at each visit and change from baseline at each visit will be listed per subject for Visit 2 (Baseline), Visit 5, and at Visit 6 (EOS). Descriptive statistics (including frequencies and percentages) for observed and change from Baseline values in I-NRS at each visit, success rate as well as a shift table will be presented by treatment group for each CI subtype and overall. Success is defined as  $\geq 4$ -point reduction from Baseline. Results from Cochran-Mantel-Haenszel test at Visit 6 (EOS) will be presented together with corresponding 95% confidence intervals.

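### The I-NRS responder comparison sets no baseline minimum, so subjects with a Visit 2 score of 0 to 3 are certain failures in every arm and the expected difference shrinks by the share of such subjects

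*SAP*

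**What the plan says.** SAP 4.6.1.3 lists I-NRS treatment success among the other secondary endpoints; it "is defined as at least a 4-point reduction in I-NRS relative to Baseline at Visit 6 (EOS". Protocol 8.2.3 describes an "11-point scale anchored at 0 representing" no itching, with 10 as the worst imaginable, collected "using the I-NRS at Visit 2 (Baseline), Visit 5, and at Visit 6 (EOS".

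Protocol 9.4.1.2 covers I-NRS in its comparison of responders: "Success rates between treatment groups will be compared at Visit 6 (EOS) using the CMH Test stratified by CI subtype", with 95% confidence intervals. SAP 9.1.3 repeats this for I-NRS: "Results from Cochran-Mantel-Haenszel test at Visit 6 (EOS) will be presented together with corresponding 95% confidence intervals". On the denominator, SAP 6.1 states: "The ITT population will be used for the analysis and presentation of all efficacy data". SAP 6.2 adds the PP population. Neither population is restricted by baseline itch, and Protocol 5.1 and 5.2 contain no itch threshold. Severity at entry is judged by scaling score and affected body surface.

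On the item, Protocol 8.2.3 has subjects rate "the worst level of itching due to CI in the past 24 hours on an 11-point scale". The form in Protocol Appendix 11 prints that question and also asks "how was your itch, on average, within the past 24 hours". The SAP does not say which item is analysed.

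**The concern.** A responder threshold of 4 points on a scale with a floor at 0 can be met only from a baseline of 4 or more. Because itch plays no part in eligibility, some subjects may enter with little or none. They stay in the denominator and are counted as failures in all three arms.

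The planned rate then mixes two quantities: how many subjects had enough itch to be able to respond, and how many of those did respond. Only the second says something about the treatment. The study is meant to supply data for dose selection and for sizing a later trial, so a difference that depends on the unknown baseline itch of this sample is hard to carry forward.

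The plan conditions on baseline elsewhere: VIIS-50 counts only sites with a baseline score of at least 3. The I-NRS responder endpoint has no counterpart. The I-NRS shift tables describe, and the MMRM compares mean change; neither gives a tested responder difference among subjects who could respond.

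**Working it through.** The plan states no I-NRS response rate, effect size or power (Protocol 9.2 and SAP 4.5 say no formal power calculation was made), so there is no planned figure to reproduce.

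**Inputs from the documents:** scale 0 to 10; success is a fall of at least 4 at Visit 6; 15 subjects per arm; 1:1:1 randomization stratified by CI subtype only; CMH stratified by subtype.

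**Assumptions:** the share f with Visit 2 I-NRS of 0 to 3 (range 0 to 60%); success of 50% (active) versus 10% (vehicle) among subjects with baseline of at least 4; subtype strata of 8 and 7 per arm where two strata are used.

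**Step 1, the floor.** The largest possible fall equals the baseline score. Baselines 0, 1, 2 and 3 allow falls of at most 0, 1, 2 and 3 points, so success is impossible. Baselines 4 to 10 can succeed.

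**Step 2, dilution.** In each arm the overall rate is (1 − f)·p + f·0 = (1 − f)·p. With the same f in both arms the difference is (1 − f)(p_A − p_V):

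| f | Active | Vehicle | Difference |
|---|---|---|---|
| 0 | 50% | 10% | 40 points |
| 10% | 45% | 9% | 36 |
| 20% | 40% | 8% | 32 |
| 40% | 30% | 6% | 24 |
| 60% | 20% | 4% | 16 |

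**Step 3, power.** The CMH chi-square without continuity correction is (a − n1·m/N)² / [n1·n2·m·(N − m)/(N²(N − 1))], where a is the active successes, m the total successes and N = n1 + n2, with critical value 3.84. For one stratum all outcomes were enumerated. The all-subject analysis uses 15 per arm at the diluted rates. The restricted analysis uses the undiluted rates, with the number evaluable per arm drawn from Binomial(15, 1 − f) and averaged over both arms. The two-strata figures are simulated.

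| f | One stratum: all / restricted | Two strata: all / restricted |
|---|---|---|
| 10% | 0.61 / 0.65 | not run |
| 20% | 0.54 / 0.59 | 0.55 / 0.59 |
| 40% | 0.39 / 0.46 | 0.40 / 0.44 |
| 60% | 0.21 / 0.29 | 0.21 / 0.26 |

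**Step 4, precision.** The Wald 95% half-width is 1.96·√(p_A·q_A/n + p_V·q_V/n), where q = 1 − p. All subjects: n = 15 and diluted rates. Restricted: n = 15(1 − f) and undiluted rates.

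- f = 20%: 1.96·√((0.40·0.60 + 0.08·0.92)/15) = 28 points, against 1.96·√((0.50·0.50 + 0.10·0.90)/12) = 33 points.
- f = 40%: 26 points against 38 (n = 9).
- f = 60%: 23 points against 47 (n = 6).

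**Step 5, unequal f.** Randomization equalizes f only in expectation. At f = 40% the SD of the between-arm difference in f is √(2·0.4·0.6/15) = 0.18, and the binomial chance that two arms of 15 differ by 3 or more such subjects is about 35%. With f of 0.3 (active) and 0.5 (vehicle) the all-subject difference is 0.50·0.7 − 0.10·0.5 = 30 points; with f reversed it is 0.50·0.5 − 0.10·0.7 = 18 points. At equal f of 0.4 it is 24.

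**The case against.** The planned all-subject rate is a coherent ITT quantity: the share of treated subjects whose itch falls by 4 points. A common floor leaves the rate ratio unchanged at equal f and does not inflate the type I error on average, so the planned test is valid. The size of f is unknown and may be zero. The endpoint is one of eight other secondary endpoints in an unpowered study. The restriction buys little power and costs precision: at f = 60% about 6 subjects per arm remain, or about 3 per subtype stratum. The planned shift tables and listings could let a reader reconstruct the restricted rates. The naming of the item and the missing table are separate, smaller matters.

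Most of this is correct, and it limits the point to interpretation. It also makes clear that the (1 − f) factor on the difference is exact only at equal f; Step 5 shows what happens otherwise. What it does not supply is a prespecified responder difference, with a confidence interval, among subjects able to respond. A reader's reconstruction would be post hoc, and would depend on the shift tables being laid out by single score, which the SAP does not state. The item question bears on the same point, because f depends on which item is used.

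**Conclusion.** The concern holds. Subjects with Visit 2 I-NRS of 0 to 3 are certain failures in every arm, and the plan neither excludes them at entry nor sets them aside in the analysis. Under randomization the expected difference is scaled by (1 − f).

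The floor is arithmetic and certain; its consequence depends on f, for which the documents give no value. Under the assumed 50% versus 10%, a 40-point difference reads as 32, 24 or 16 points at f of 20%, 40% or 60%, and as 40 if f is 0. The case for change is a rate that can be interpreted, not power: the gain with two strata is about 4 to 5 percentage points. The change is worth making but is not critical, and no primary or key secondary conclusion depends on it.

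**What to change.** Before unblinding, amend SAP 4.6.1.3 and 9.1.3 as follows.

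- Compare each active arm with vehicle on I-NRS success (CMH by CI subtype, with 95% confidence interval) in ITT subjects with Visit 2 I-NRS of at least 4, and likewise in PP.
- Name the item. Protocol 8.2.3 describes worst itch; the SAP should say so, and say how the average-itch item on the form is used, if at all.
- Report the number evaluable per arm, and keep the all-subject success rate as a supportive display.
- Leave the MMRM of I-NRS change in all subjects.
- Add the I-NRS CMH table to SAP Appendix 2. SAP 9.1.3 promises the test, but the appendix lists only success-rate tables and figures for I-NRS, while VIIS and IGA each have CMH tables.

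The cost is one baseline condition and one table. The Visit 2 score is already collected, and because it precedes treatment the restriction keeps the comparison randomized. The drawback is a smaller denominator, about 15 × 0.6 = 9 evaluable per arm at f = 40% and 15 × 0.4 = 6 at f = 60% before stratification, with the wider intervals shown above. If f is near zero the two analyses coincide.
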